5 STUDY POPULATION

Prospective approval of protocol deviations to recruitment and enrollment criteria, also known as protocol waivers or exemptions, is not permitted.

- Study participant has any medical or psychiatric condition or significant laboratory abnormality that, in the opinion of the investigator, could jeopardize or would compromise the study participant's ability to participate in this study.
- 2. Study participant has a history of alcohol use disorder or other substance use disorder (as per Diagnostic and Statistical Manual of Mental Disorders-5 [American Psychiatric Association, 2013]) within the previous 12 months before Screening (Visit 1).

- 4. Study participant with a known tuberculosis (TB) infection, at high risk of acquiring TB infection, or latent tuberculosis infection (LTBI), or current or history of nontuberculous mycobacterial infection (NTMBI).
- 5. Study participant has a clinically relevant active infection or a history of serious infection (resulting in hospitalization or requiring IV antibiotic treatment) within 6 weeks before the Baseline Visit (Visit 2
- 6a. The study participant previously participated in any rozanolixizumab MG study and met any mandatory withdrawal criteria (unless the reason is directly related to MG0020 participation) or mandatory study drug discontinuation criteria.

Prior or concomitant therapy

- 7a. Study participant has received a live vaccination within 4 weeks before starting treatment, or a BCG vaccine within 1 year before starting treatment; or intends to have a live vaccination during the course of the study or within 8 weeks following the last dose of rozanolixizumab.
- 8. Study participant received treatment with rituximab or other anti-CD20 or anti-CD19 medication within before the Baseline Visit (Visit 2
- 9a. Study participant has received treatment with IVIg, SC Ig, or PEX within before the Baseline Visit (Visit 2 treatment with efgartigimod within before the Baseline Visit; treatment with eculizumab before the Baseline Visit; treatment with ravulizumab within before the Baseline Visit or prior treatment with cyclophosphamide.

Diagnostic assessments

- 10. Study participant has absolute neutrophil count <1500 cells/mm³ at Screening (Visit 1).
- 11. Study participant with severe (defined as Grade 3 on the MG-ADL scale) weakness affecting oropharyngeal or respiratory muscles, or who has myasthenic crisis or impending crisis.
- 12. Study participant has renal impairment, defined as glomerular filtration rate less than 30mL/min/1.73m² at Screening (Visit 1).
- 13. Study participant has 12-lead electrocardiogram (ECG) at Screening (Visit 1) with findings considered to be clinically significant upon medical review. The clinical significance of the findings needs to be assessed by the investigator to determine eligibility.
- 14. Study participant has >3.0xULN of any of the following: alanine aminotransferase (ALT), aspartate aminotransferase (AST), or alkaline phosphatase (ALP) at Screening (Visit 1).
 - If participant has >upper limit of normal (ULN) for ALT, AST, or ALP that does not meet the exclusion limit at Screening (Visit 1), repeat the tests, if possible, before dosing to ensure there is no further ongoing clinically relevant increase.

- For participants with a Baseline result >ULN for ALT, AST, ALP, or total bilirubin, a
 Baseline diagnosis and/or the cause of any clinically meaningful elevation must be
 recorded in the CRF.
- 15. Study participant has bilirubin >1.5xULN at Screening (Visit 1) (unless confirmed Gilbert's syndrome). If participant has elevations only in total bilirubin, the fractionate bilirubin needs to be checked, to identify possible undiagnosed Gilbert's syndrome (ie, direct bilirubin <35%).
- 16. Current unstable liver or biliary disease, at Screening (Visit 1), per investigator assessment defined by the presence of ascites, encephalopathy, coagulopathy, hypoalbuminemia, esophageal or gastric varices, persistent jaundice, or cirrhosis. NOTE: with exception of stable hepatobiliary conditions (including Gilbert's syndrome, asymptomatic gallstones).
- 17. Presence of Hepatitis B surface antigen (HBsAg) or positive Hepatitis C antibody test result at Screening (Visit 1). Note: a study participant with a positive hepatitis C antibody test due to prior resolved disease can be enrolled only if a confirmatory negative Hepatitis C RNA test is obtained.
- 18. Study participant tests positive for human immunodeficiency virus at Screening (Visit 1).
- 19a. Study participant has active malignant neoplastic disease or history of malignant neoplastic disease within 5 years of study entry before Screening (Visit 1) (except for basal or squamous cell carcinoma of the skin or carcinoma in situ of the uterine cervix that have been definitively treated with standard of care approaches or thymoma that did not require chemotherapy and/or radiotherapy after removal).

Other

20. Study participant has a lifetime history of

as indicated by a positive

response (Yes) to either Question 4 or Question 5 of the Columbia-Suicide Severity Rating Scale (C-SSRS) at Screening (Visit 1).

5.3 Lifestyle restrictions

There are no lifestyle restrictions during the study unless deemed to interfere with compliance with the protocol as deemed by the investigator.

The use of medicinal cannabidiols and medicinal marijuana (prescribed by a Physician) is permitted.

5.4 Screen failures

Screen failures are defined as participants who consent to participate in the clinical study but are not subsequently allocated to treatment during the Training Period. A minimal set of screen failure information is required to ensure transparent reporting of screen failure participants to meet the Consolidated Standards of Reporting Trials publishing requirements and to respond to queries from regulatory authorities. Minimal information includes demography, screen failure details, eligibility criteria, and any serious adverse event (SAE).

Individuals who do not meet the criteria for participation in this study (screen failure) may be rescreened once. Additional rescreening of these individuals following upfront discussion with

the medical monitor or study physician might be allowed. Rescreened study participants should be assigned a new participant number for rescreening.

If a study participant has 1 isolated test result outside the specific range which is deemed clinically nonsignificant, the abnormal value may be rechecked at the discretion of the investigator, following consultation with the sponsor's medical monitor or study physician. If the normalization of the test result occurs within the Screening Period, then no other Screening procedures need to be repeated.

6 STUDY TREATMENTS

Study treatment is defined as any investigational treatment(s), marketed product(s), placebo, or medical device(s) intended to be administered to a study participant according to the study protocol. Treatments in this study vary based on either an approved label in a region (US) or a proposed dosing under review in a region (Europe and Canada).

6.1 Treatments administered

| Study treatment name | Treatment | Treatment |
|--------------------------------------|--|--|
| Intervention name | Rozanolixizumab | Rozanolixizumab |
| Type | Biologic | Biologic |
| Dose formulation | | |
| Unit dose strength(s) | | |
| Dosage level(s) US | fixed doses of for study participants <50kg, for study participants ≥50kg to <100kg or for study participants ≥100kg. | fixed doses of for study participants <50kg, for study participants ≥50kg to <100kg or for study participants ≥100kg. |
| Dosage level(s) Europe and Canada | fixed doses of for participants $\geq 35 \mathrm{kg}$ to $< 50 \mathrm{kg}$, for study participants $\geq 50 \mathrm{kg}$ to $< 70 \mathrm{kg}$, for study participants $\geq 70 \mathrm{kg}$ to $< 100 \mathrm{kg}$ or for study participants $\geq 100 \mathrm{kg}$. | fixed doses of for participants $\geq 35 \mathrm{kg}$ to $< 50 \mathrm{kg}$, for study participants $\geq 50 \mathrm{kg}$ to $< 70 \mathrm{kg}$, for study participants $\geq 70 \mathrm{kg}$ to $< 100 \mathrm{kg}$ or for study participants $\geq 100 \mathrm{kg}$. |
| Route of administration | Subcutaneous infusion via syringe driver | Subcutaneous infusion via manual push |
| Use | Experimental | Experimental |
| IMP and NIMP | IMP | IMP |
| Sourcing | Provided centrally by the sponsor | Provided centrally by the sponsor |

Confidential Page 37 of 124

| Packaging and labeling | Packaging will be described in the IMP Handling Manual. Packaging will be labeled as required per country requirement. | Packaging will be described in the IMP Handling Manual. Packaging will be labeled as required per country requirement. |
|-------------------------------------|--|--|
| Current/Former name(s) or alias(es) | UCB7665 | UCB7665 |

Abbreviations: IMP=investigational medicinal product; NIMP=noninvestigational medicinal product

6.1.1 Medical devices

Other medical devices (not manufactured by or for UCB) are provided for SC infusion. Medical devices used as part of this clinical study will be used within their approved intended use. Proof of registration will be kept on file and available for inspection.

Instructions for use are provided in the IMP Handling Manual.

All adverse device effects (ADEs), serious adverse device effects (SADEs), and device deficiencies (including malfunctions, use errors, and inadequate labeling) shall be documented and reported by the investigator throughout the study (see Section 8.3.9) and appropriately managed by the sponsor.

6.2 Preparation, handling, storage, and accountability requirements

Details on the preparation of study medication for infusion, methods of administration, rate of infusion, as well as supply of kits for self-administration are provided in the IMP Handling Manual.

The investigator or designee and the study participant (at home self-administration visits) must confirm that appropriate temperature conditions have been maintained during transit for all study medication received, and any discrepancies are reported and resolved before use of the study medication.

Only participants enrolled in the study may receive study medication. All study medication must be stored in a secure, environmentally controlled, and monitored (manual or automated) area in accordance with the labeled storage conditions, with access limited to the investigator or authorized site staff and to the study participant or caregiver during home self-administration visits.

The investigator, institution, or the head of the medical institution (where applicable) is responsible for study medication accountability, reconciliation, and record maintenance (ie, receipt, reconciliation, and final disposition records).

In case an out-of-range temperature is noted, it must be immediately reported as per instructions contained in the IMP Handling Manual.

The investigator (or designee) will instruct the participant to store the study medication following the instructions on the label and in the IMP Handling Manual.

Further guidance and information for the final disposal of unused study medication are provided in the Study Reference Manual.

6.2.1 **Drug/Device accountability**

A Drug/Device Accountability form will be used to record study medication dispensing and return information on a by-participant basis and will serve as source documentation during the The investigator (or designee) is responsible for retaining all used, unused, and partially used containers of study medication until returned or destroyed.

The investigator may assign some of the investigator. course of the study. Details of any study medication lost, damaged (due to breakage or wastage),

The investigator must ensure that the study medication is used only in accordance with the protocol.

Periodically, and/or after completion of the clinical phase of the study, all used (including empty or partially used containers), unused, damaged, and/or expired study medication must be reconciled and either destroyed at the site according to local laws, regulations, and UCB standard operating procedures or returned to UCB (or designee). Investigational medicinal product intended for the study cannot be used for any other purpose than that described in this protocol.

Measures to minimize bias: randomization and blinding 6.3

This is an open-label study without blinding; however, the order that a specific intervention is to be taken by a participant will be assigned using an interactive response technology (IRT). Potential bias will be reduced using central randomization. The IRT will be used for assigning eligible participants to a treatment sequence (see Table 1-1) based on a predetermined production randomization and/or packaging schedule provided by UCB (or designee). The randomization schedule will be produced by the IRT vendor. The IRT will generate individual assignments for kits of study medication, as appropriate, according to the visit schedule.

To enroll a study participant (Visit 1), the investigator or designee will contact the IRT and provide brief details about the participant to be enrolled. Each participant will receive a 5-digit number assigned at Screening that serves as the participant identifier throughout the study. The participant number will be required in all communication between the investigator or designee and the IRT regarding a particular participant. Participant numbers and kit numbers will be tracked via the IRT.

At Visit 2 (Baseline), the investigator or designee will contact the IRT to confirm participant's eligibility (including the participant's body weight as recorded at Screening). The IRT will allocate kit numbers to the participant.

At Visit 8, in order to randomize a participant to a treatment sequence (see Table 1-1), the investigator or designee will contact the IRT and provide brief details about the participant to be randomized. The IRT will automatically inform the investigator or designee of the participant's randomization number. The IRT will allocate kit numbers to the participant based on the participant number during the course of the study. The randomization number must be

Confidential Page 39 of 124 incorporated into the CRF. The site will record the intervention assignment on the applicable CRF, if required.

6.4 Treatment compliance

Participants must return all used and unused vials as well as all equipment and ancillary materials used for IMP administration at Visit 13 () and Visit 19 (). Drug accountability must be done in the participant's presence in order to obtain explanations regarding discrepancies in compliance with the dosing regimen. Drug accountability must be recorded on the Drug Accountability form.

The intended dose is based on Table 1-2 (the acceptable administered range is $\geq 80\%$ of the total volume used based on visual inspection of the residual IMP at site).

For home self-administrations, the study participant should provide a respective photographic documentation to allow the HCP to assess the volume of IMP administered, using the mobile phone provided by UCB. Further details are provided in the IMP Handling Manual.

If a participant is found to be persistently noncompliant (eg, does not comply with visit schedule or protocol procedures), the sponsor, in conjunction with the investigator, will make a decision as to whether the participant should be withdrawn from the study.

6.5 Concomitant medication(s)/treatment(s)

6.5.1 Permitted concomitant treatments (medications and therapies)

Concomitant medications listed in Table 6-1 are permitted during the study for the treatment of gMG. With the exception of corticosteroids and acetylcholinesterase inhibitors, the dose of permitted concomitant medications should be maintained, if possible.

If a study participant receives a COVID-19 vaccine, the product name and date of administration(s) should be captured in the CRF as a concomitant medication.

| Table 6-1: | Permitted | concomitant | treatments |
|------------|-----------|-------------|------------|
|------------|-----------|-------------|------------|

| Permitted medications | Dose |
|---|--|
| Oral corticosteroids (eg, prednisolone) | No specific requirements |
| Methotrexate | ≤30mg/week |
| Mycophenolate mofetil | ≤3g/day |
| Cyclosporine ^a | ≤5mg/kg/day for unmodified ≤4mg/kg/day for modified (microemulsion) |
| Azathioprine | ≤3mg/kg/day |
| Cholinesterase inhibitors | ≤600mg pyridostigmine/day |
| Tacrolimus ^b | ≤5mg/day |

Doses higher than listed are permissible if trough level is ≤300ng/mL.

Confidential

b If the total daily weight-based dose is >5mg, then a plasma trough level should be checked to ensure study participant is not above the recommended therapeutic range.

6.5.2 Prohibited concomitant treatments (medications and therapies)

The following concomitant medications are prohibited during the study:

- All biologics, including rituximab
- Cyclophosphamide
- Pimecrolimus
- IPP-201101 (LupuzorTM)
- Immunoadsorption
- Vinca alkaloids (vincristine, vinblastine)

6.5.3 Treatments specific to NMJ interference

Treatments that could interfere with the function of the NMJ (and which therefore could impair study participants with gMG) include, but are not limited to, the following medications:

- Botulinum toxin
- Aminoglycoside antibiotics
- Tetracycline antibiotics
- Penicillamine
- Magnesium

For a more detailed list please refer to the Myasthenia Gravis Foundation of America (MGFA) medication list (https://myasthenia.org/What-is-MG/MG-Management/Cautionary-Drugs). The benefit-risk of starting these medications should be carefully considered by the investigator, and where possible, the investigator will discuss with the medical monitor and/or sponsor's study physician before initiating therapy that can affect the NMJ.

6.5.4 Rescue medication

The study site will supply rescue therapy that will be obtained locally. Rescue therapy will be given as per standard of care and at the discretion of the investigator. Study participants who continue to experience moderate to severe symptoms despite treatment with rozanolixizumab may receive treatment with the following as rescue therapy:

- Intravenous Ig (ATC code: [Immunoglobulins, normal human])
- Subcutaneous Ig (ATC code: [Immunoglobulins, normal human])
- Plasma exchange or plasmapheresis
- Intravenous corticosteroids at a higher dose than previous oral dose (ATC code: [Corticosteroids for systemic use, plain])

Study participants who received treatment with rescue therapy will be withdrawn from the study.

The date and time of rescue medication administration as well as the name and dosage regimen of the rescue medication must be recorded.

6.6 Dose modification

There is no dose modification allowed in this study, ie, study participants must maintain their dose (based on body weight as recorded at Screening) throughout.

6.7 Criteria for study hold or dosing stoppage

Not applicable.

6.8 Treatment after the end of the study

Study participants who have completed all Treatment Periods (including the End of Treatment Visit) will have the option to subsequently move, at the discretion of the investigator, into either a post-trial access program for rozanolixizumab (if available according to local guidance) or on to commercially available rozanolixizumab.

[figure not shown]
7 DISCONTINUATION OF STUDY MEDICATION AND PARTICIPANT DISCONTINUATION/WITHDRAWAL

7.1 Discontinuation of study medication

7.1.1 Liver chemistry stopping criteria

Discontinuation of study treatment for abnormal liver function should be considered by the investigator when a participant meets one of the conditions outlined Figure 7-1 and Figure 7-2 or if the investigator believes that it is in best interest of the participant.

Figure 7-1: Liver Chemistry Stopping Criteria and Increased Monitoring Algorithm

[figure not shown]
(Note: INR value not applicable to patients on anticoagulants)

ALT=alanine aminotransferase; AST=aspartate aminotransferase; INR=international normalized ratio; SAE=serious adverse event; ULN=upper limit of normal

Confidential Page 42 of 124

Treatment with study medication may be continued with increased monitoring if a study participant meets one of the criteria outlined in Figure 7-2.

Figure 7-2: Liver Chemistry Increased Monitoring Algorithm with Continued Study Intervention for Participants with ALT ≥3xULN but <8xULN

ALT=alanine aminotransferase; AST=aspartate aminotransferase; bili=bilirubin; INR=international normalized ratio; SAE=serious adverse event; ULN=upper limit of normal

Specific assessments and follow-up actions for potential drug-induced liver injury (PDILI) are provided in Appendix 6 (Section 10.6).

7.1.2 **Temporary IMP discontinuation**

Study participants must be TEMPORARILY discontinued from the IMP if any of the following events occur:

- 1. Symptomatic cases of confirmed COVID-19 infection. The IMP may be restarted if clinically appropriate when signs and symptoms have resolved and in agreement with local guidelines.
- 2. Study participant has a first diagnosis of suspected aseptic meningitis. The IMP may be restarted if clinically appropriate when signs and symptoms have resolved. Refer to Section 71.3 for permanent discontinuation criteria (criterion #9).

Study participants may be TEMPORARILY discontinued from the IMP if the following events occur:

1. The study participant develops an event of hypogammaglobulinemia with a serum total IgG of ≤ 1 g/L irrespective of infection. When the IgG level reaches ≥ 2 g/L, the study participant may be allowed to continue treatment with IMP (see Appendix 13 [Section 10.13.2]).

- 2. The study participant develops a nonserious persisting or recurrent infection with serum total IgG level between ≥1 and <2g/L. Upon resolution of infection and the IgG returning to level of ≥2g/L, the study participant may be allowed to resume treatment with the IMP (see Appendix 13 [Section 10.13.2]).
- 3. Asymptomatic or suspected cases of COVID-19 infection. The IMP may be restarted when clinically appropriate as deemed by the investigator and in agreement with local guidelines.
- 4. Study participant may be temporarily discontinued from study medication at the discretion of the investigator in cases deemed strictly necessary for the participant's medical care. Efforts should be made to keep the length of temporary discontinuation to a minimum.

The investigator should discuss with the medical monitor and/or sponsor's study physician before reinitiating the IMP. As appropriate, virtual assessments could continue (eg, AE collection, patient-reported outcome [PRO] assessments as per contingency measures described in Section 8).

If IMP treatment is resumed, the study participant should continue with the next dose as previously scheduled and subsequently follow the visit schedule as described in the protocol. The CRF should be completed accordingly, including the information if the visit was impacted by COVID-19 infection.

The date and reason for dose hold of rozanolixizumab is to be recorded on each study participant's CRF.

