7.1.3 Study medication permanent discontinuation criteria

Study participants **must** permanently discontinue study medication if any of the following events occur:

- 1. Study participant develops an illness that would interfere with his or her continued participation.
- 2a. Study participant has new onset or reoccurrence of malignant neoplastic disease (except for superficial basal or squamous cell carcinoma of the skin not requiring targeted biological therapy, chemotherapy or radiation).3. Study participant experiences an infective episode including but not limited to bacteremia or sepsis, infectious meningitis, septic arthritis, osteomyelitis, complicated pneumonia, or visceral abscess, which may or may not result in hospitalization during a Treatment Period (Appendix 13 [Section 10.13.2]). This list is not intended to be all inclusive, and the investigator is expected to apply their judgment on continuing IMP based on the clinical situation.
- 4. Study participant meets PDILI permanent discontinuation criteria.
- 5. Study participant has a TB test that is confirmed positive or any further evidence suggestive of potential TB infection (ie, exposure) and further examinations result in a diagnosis of active TB or LTBI.
- 6. If a NTMBI is identified during a study, the same withdrawal procedures as those used for an active TB infection identified during the study should be followed.

- 7. Study participant has an AE of severe or serious infusion-related reaction, hypersensitivity, or anaphylactic reaction requiring corticosteroid and/or epinephrine therapy (Sampson et al, 2006; Appendix 13 [Section 10.13.1]).
- 8. Study participant takes prohibited concomitant medications as defined in this protocol.
- 9. Study participant has a recurrence of aseptic meningitis (see also Appendix 14 [Section 10.14]).
- 10. Study participant has as indicated by a positive response (Yes) to either Question 4 or Question 5 of the "Since Last Visit" version of the C-SSRS. The study participants should be referred immediately to a mental healthcare professional.

Study participants **may** permanently discontinue rozanolixizumab at the discretion of the investigator (following consultation with the sponsor's medical monitor or study physician if necessary) if the study participant is noncompliant or becomes unable to comply with the study procedures or medications in the opinion of the investigator.

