10.6 Appendix 6: Liver safety – suggested actions and follow-up assessments

Participants with PDILI must be assessed to determine if study medication must be discontinued. In addition, all concomitant medications and herbal supplements that are not medically necessary should also be discontinued.

Investigators should attempt to obtain information on study participants in the case of study medication discontinuation to complete the final evaluation.

Study participants with PDILI should not be withdrawn from the study until investigation and monitoring are complete. All results of these evaluations and observations, as well as the reason(s) for study medication discontinuation and/or participant withdrawal (if applicable), must be recorded in the source documents. The CRF must document the primary reason for discontinuation of study medication.

A specific monitoring plan must be agreed between the UCB study physician and the investigator for study participants who have ALT >5 ULN. The monitoring plan should include any necessary follow-up assessments (until resolution of the abnormal laboratory values).

Phase 3-4 liver chemistry stopping criteria are designed to assure participant safety and to evaluate liver event etiology.

Table 10-2: Phase 3-4 liver chemistry stopping criteria and follow-up assessments

| | Liver chemistry stopping criteria |
|--------------------------|---|
| ALT-absolute | ALT ≥8x ULN |
| ALT increase | ALT ≥5xULN but <8xULN persists for ≥2 weeks |
| | ALT $\geq 3x$ ULN but $\leq 5x$ ULN persists for ≥ 4 weeks |
| Bilirubin ^{a,b} | ALT ≥3xULN and bilirubin ≥2xULN (>35% direct bilirubin) |
| INR ^b | ALT ≥3xULN and INR >1.5, if INR measured |
| Cannot | ALT ≥ 5 xULN but ≤ 8 xULN and cannot be monitored weekly for ≥ 2 weeks |
| monitor | ALT ≥3xULN but <5xULN and cannot be monitored weekly for ≥4 weeks |
| Symptomatic ^c | ALT ≥3xULN associated with symptoms (new or worsening) believed to be related to liver injury or hypersensitivity |
| 90chusik | Aicait. |

Table 10-2: Phase 3-4 liver chemistry stopping criteria and follow-up assessments

| assessments | | | | |
|--|--|--|--|--|
| Liver chemistry stopping criteria | | | | |
| Suggested actions and follow-up assessments | | | | |
| Actions | Follow-up assessments | | | |

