| Immediately discontinue study medication. Report the event to UCB within 24 hours. Complete the liver event CRF, and complete a SAE data collection tool if the event also met the criteria for a SAE. Perform liver chemistry follow-up assessments. Monitor the participant until liver chemistry test abnormalities resolve, stabilize, or return to Baseline (see MONITORING). Do not restart/rechallenge participant with study medication unless allowed per protocol and UCB approval is granted. If restart/rechallenge is not allowed per protocol or not granted, permanently discontinue study medication, and continue participant in the study for any protocol-specified follow-up assessments. Consider the need for a toxicology screening. MONITORING: For bilirubin or INR criteria Repeat liver chemistry tests (include ALT, AST, ALP, bilirubin) and perform liver event follow-up assessments within 24 hours. Monitor participant twice weekly until liver chemistry test abnormalities resolve, stabilize, or return to Baseline. A specialist or hepafology consultation is recommended. For all other criteria Repeat liver chemistry tests (include ALT, AST, ALP, bilirubin) and perform liver chemistry follow-up assessments within 24 to 72 hours. Monitor participants weekly until liver chemistry abnormalities resolve, stabilize, or return to Baseline. | Viral hepatitis serology^d Obtain INR and recheck with each liver chemistry assessment until the transaminases values show downward trend Only in those with underlying chrone hepatitis B at study entry (identified by positive HBsAg): quantitative hepatitis B DNA and hepatitis delta antibody^c Obtain blood sample for PK analysis after the most recent dose^f Serum CPK and LDH Fractionate bilirubin, if total bilirubin ≥2xULN Obtain complete blood count with differential to assess eosinophilia Record the appearance or worsening of clinical symptoms of liver injury (eg, fatigue, nausea, vomiting, right upper quadrant pain), or hypersensitivity, on the AE CRF Record use of concomitant medications (including acetaminophen, herbal remedies, and other overthe-counter medications) on the concomitant medications CRF. Record alcohol use on the liver event alcohol intake CRF Exclude pregnancy For bilirubin or INR criteria: Anti-nuclear antibody, anti-smooth muscle antibody, Type 1 anti-liver kidney microsomal antibodies, and quantitative total IgG or gamma globulins. Serum acetaminophen adduct HPLC assay (quantifies potential acetaminophen contribution to liver injury in participants with definite or likely acetaminophen use in the preceding week [James et al, 2009]). NOTE: Not required in China. Liver imaging (ultrasound, magnetic resonance, or computerized tomography) and/or liver biopsy to evaluate liver disease; complete liver imaging and/or liver biopsy complete liver imagi | | | |

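### For results that meet the liver chemistry stopping criteria, the protocol gives the same action different force: considered in Section 7.1.1, immediate in Table 10-2, and labelled both suggested and required

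*Protocol*

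**What the plan says.** Four places in the protocol set the force of the liver stopping rule, and a fifth deals with permanent discontinuation.

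- **Section 7.1.1**, whose title is the liver chemistry stopping criteria, leads into Figures 7-1 and 7-2 with: "Discontinuation of study treatment for abnormal liver function should be considered by the investigator when a participant meets one of the conditions". It then adds: "Treatment with study medication may be continued with increased monitoring if a study participant meets one of the criteria outlined in Figure 7-2".
- **Appendix 6, Table 10-2** lists the stopping criteria and gives as the action: "Immediately discontinue study medication. Report the event to UCB within 24 hours". The appendix title describes its content as "suggested actions and follow-up assessments", and the same phrase heads the action rows of the table. The appendix opens with: "Participants with PDILI must be assessed to determine if study medication must be discontinued". Table 10-2 also bars restart unless the protocol allows it and the sponsor approves; failing either, discontinuation becomes permanent.
- **Table 10-1, note a** (Appendix 2) describes the actions after a liver stopping or monitoring event as *required*, and cites both Section 7.1.1 and Appendix 6 for them. SAP Table 4-4 repeats this note.
- **Appendix 6, Table 10-3** covers increased monitoring with continued treatment. If such a participant later meets a stopping criterion, it directs the site to Section 7.1.1.
- **Section 7.1.3** lists events for which participants must "permanently discontinue study medication if any of the following events occur". Criterion 4 reads: "Study participant meets PDILI permanent discontinuation criteria". No list under that name appears in the visible text.

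**The concern.** A stopping rule should tell the investigator what follows once its criterion is met. Here the section that carries the rule's name leaves the decision to judgement, while the table holding the detailed criteria gives an instruction to act at once. The labels on that instruction point in opposite directions, and one cross-reference leads from the stricter place back to the looser one. A site, a monitor or an auditor asking whether continued dosing after a stopping result was a protocol deviation would get a different answer depending on the page consulted.

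What is at stake is participant safety: Appendix 6 itself gives safety as the first purpose of the stopping criteria. A lesser consequence is that a decision to stop or continue can determine who reaches self-administration at Visits 13 and 19, which SAP Section 3 requires for the Full Analysis Set (FAS).

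**Working it through.** The point concerns wording, and the plan states no figure to reproduce. The check sets the passages side by side for one result and then follows the cross-references.

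**One result under each passage.** Take ALT at or above 8 times the upper limit of normal, the first stopping criterion in Table 10-2.

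| Place | Reading for this result |
|---|---|
| Section 7.1.1, lead-in | Investigator considers stopping; continuing is not excluded |
| Table 10-2, action row | Stop immediately and report within 24 hours |
| Title of Appendix 6 and heading of the action rows | The action is suggested |
| Table 10-1, note a | The action is required |
| Table 10-3, if the participant was already under monitoring | Go to Section 7.1.1, hence back to consideration |
| Section 7.1.3, criterion 4 | Permanent stop is mandatory, if this result counts as one of the undefined criteria |

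The first two rows differ in force for the same event. The next two disagree on how binding the Table 10-2 instruction is. The Table 10-3 row shows that Appendix 6 does not simply override Section 7.1.1, because it defers to it.

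**Limits of the conflict.** For results in the increased-monitoring tier (ALT at least 3 but below 8 times the upper limit, with the other conditions of Table 10-3), Section 7.1.1 and Table 10-3 both allow treatment to continue. The two are consistent there. The conflict is confined to results that meet the stopping criteria.

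**Section 7.1.3.** Table 10-2 separates stopping from permanent stopping: the stop becomes permanent only if restart is not allowed or not granted. Criterion 4 may be meant to refer to that outcome, or to a list of its own. The visible text does not say. The two can stand together, so what is shown is a reference without a target.

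**The figures.** Figures 7-1 and 7-2 could not be seen, and that is not held against the plan. Their content would not remove the conflict. If Figure 7-1 makes stopping mandatory, it disagrees with the sentence that introduces it; if it leaves stopping to judgement, it disagrees with Table 10-2.

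**Reach into the analysis.** The Schedule of Activities marks clinical chemistry at Visits 1, 2, 3, 8, 14, 20 and 21. Randomization is at Visit 8. Between randomization and Visit 19, only the samples at Visits 8 and 14 are scheduled, so few planned results could alter FAS membership; unscheduled tests could add some. One participant is 1/30 = 3.3% of a 30-participant FAS, but 30 is a planned minimum (Protocol Section 9.9), and SAP Section 4.2.2 reports that more participants than planned could use both methods. The percentage is therefore an upper figure per affected participant, and the documents give no liver event rate to multiply it by.

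**The case against.** The strongest reply is that these passages are layers of one process. The lead-in of Section 7.1.1 covers two figures at once, one of them about continued treatment, so a verb of obligation could not have fitted both. Section 7.1.1 points to Appendix 6 for specific actions, the action steps may be in the unseen Figure 7-1, and Appendix 6 also begins with an assessment. This explains how the wording arose. It does not settle the status of a result that meets a stopping criterion: nothing gives the appendix precedence, its own heading says suggested, and Table 10-3 sends the reader back.

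Three stronger readings are tempting and are not supported.

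- A reader might infer a three-way contradiction that includes Section 7.1.3. That section concerns permanent discontinuation, and the restart clause in Table 10-2 gives criterion 4 a plausible meaning. Only the missing target is established.
- A reader might infer that sites will take opposite actions on the same result. The oversight provisions limit this: safety tests are run centrally as a rule, a stopping event is reported to the sponsor within 24 hours, restart needs sponsor approval, and ALT above 5 times the upper limit calls for a monitoring plan agreed with the sponsor's study physician. The text permits divergence; it does not show that divergence is likely.
- A reader might infer that unsupervised home dosing makes the problem acute, or that the primary analysis is materially exposed. No scheduled chemistry falls on a home visit (Visits 10 to 12 and 16 to 18), participants with ALT, AST or ALP above 3 times the upper limit at Screening are excluded, and Section 7.2 allows replacement of participants who discontinue.

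**Conclusion.** The point holds in a limited form. For results meeting the liver chemistry stopping criteria, the protocol attaches different force to the same action in Section 7.1.1, Table 10-2, its heading and the Table 10-1 note, and Table 10-3 closes the loop without resolving it. Criterion 4 of Section 7.1.3 is a separate, smaller matter: an unresolved cross-reference.

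The conclusion assumes that the stopping conditions in Figure 7-1 are those of Table 10-2. The shared name, and the Table 10-1 note citing both places for the same criteria, support this, but the figure was not available. It also assumes that no figure defines the criteria named in criterion 4.

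The reason to correct this is participant safety. The effect on FAS membership and on the primary estimate is minor and not quantifiable from the documents.

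**What to change.** Reconcile Section 7.1.1 (lead-in and figures), note a to Table 10-1, and Appendix 6 (title, the heading above the actions, Table 10-2 and Table 10-3) so that each stopping criterion in Table 10-2 carries one stated status wherever it is mentioned, and so that the reference from Table 10-3 leads to text with that same status. Point criterion 4 of Section 7.1.3 to a named list, consistent with the restart clause in Table 10-2. Carry any change to the Table 10-1 note into its copy in SAP Table 4-4. Which status is right is a clinical decision for the sponsor, and this review takes no position on it.

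The cost is protocol wording, with a matching edit to one SAP table note. Sample size, visit schedule and planned analyses are unaffected.
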